7.5 Blinding

In compliance with applicable regulations, in the event of a suspected, unexpected, serious adverse reaction (SUSAR; see Section 9.6.1.5) related to the blinded treatment, the subject's treatment code will usually be unblinded before reporting to the health authorities, ethic committees and investigators (see Section 9.6.1.4).

Emergency unblinding by the investigator¹¹⁰

In case of emergency unblinding for a serious adverse event (SAE), investigators will use the IVRS/IWRS to unblind a subject.

7.6 Drug logistics and accountability

At Visit 6 (Day 30), subjects will return their diaries, all remaining study drug, and empty packaging. The diaries will be reviewed to assess study drug accountability, and study drug for the remaining 30 days of treatment will be dispensed.

At Visit 8 (Day 60), subjects will return their diaries, all remaining study drug, and empty packaging. The diaries will be reviewed to assess study drug accountability, and no additional study drug will be dispensed.¹¹¹

Details regarding storage conditions for nifurtimox are provided in the Investigators' Brochure.¹¹² Additional details regarding storage conditions may be provided separately. Nifurtimox and the matching placebo are not to be stored above 25°Celsius.

¹⁰⁶ As per amendment 2

¹⁰⁷ Diaries capturing information on daily dosing to be provided to subjects; diary added as appendix in Section 16 (Amendment 1)

¹⁰⁸ Text re: possible discoloration of urine due to riboflavin added per Modification 4 (Amendment 1)

¹⁰⁹ Text added for clarity regarding study drug dosing in relation to PK assessments (Amendment 1)

¹¹⁰ Emergency unblinding added as of amendment 2

¹¹¹ Text added for clarity regarding diaries and return of study drug and packaging (Amendment 1)

¹¹² Revised since Investigators' Brochure became available to serve as the reference document for nifurtimox (Amendment 1)

	Integrated Clinical Study Protocol	
	BAY A2502 / 16027	
03 NOV 2020	Version 11.0	Page: 45 of 259

All study drugs will be stored at the investigational site in accordance with Good Clinical Practice (GCP) and GMP requirements and the instructions given by the clinical supplies department of the sponsor (or its affiliate/Contract Research Organization [CRO]), and will be inaccessible to unauthorized personnel. Special storage conditions and a complete record of batch numbers and expiry dates can be found in the sponsor's study file; the site-relevant elements of this information will be available in the investigator site file. On the day of receipt, the responsible site personnel will confirm receipt of study drug via IVRS/IWRS. The site personnel will use the study drug only within the framework of this clinical study and in accordance with this protocol. Receipt, distribution, return and destruction (if any) of the study drug must be properly documented according to the sponsor's agreed and specified procedures.

Written instructions on medication destruction will be made available to affected parties as applicable.

If performing drug accountability implies a potential risk of contamination, a safety process/ guidance for handling returned drug will be provided.

7.7 Treatment compliance

Study site personnel will review diaries and¹¹³ perform a tablet count of all returned study medication to determine treatment compliance. Any discrepancies between actual and expected amount of returned study medication must be discussed with the subject at the time of the visit, and any explanation must be documented in the source records.

Treatment compliance will also be assessed during the telephone contacts at Visits 4, 5, and 7 (see Section 16.1).¹¹⁴

7.8 Treatment in part 2 (CHICO SECURE)

No study drug will be administered in the LTFU.

At their discretion, investigators may choose the appropriate drug for subjects assessed as requiring antitrypanosomal treatment during the course of LTFU. This treatment is not considered as study drug.

8. Non-study therapy

8.1 **Prior and concomitant therapy**

Information on prior and concomitant medications used during the study is useful to support PK evaluations as planned in this study in order to evaluate/exclude potential drug-drug interactions (part 1).

All prior and concomitant medications administered from the time the informed consent/assent is signed until the last follow-up visit will be recorded in the subject's source documentation file and reported in the eCRF. Information on concomitant medication use will also be recorded on the Phone Contact Form which will be completed during the telephone assessments at Visits 4, 5, and 7 in part 1 of the study and at FU Visits 2 and 4 in

¹¹³ Text added for clarity re: diaries (Amendment 1)

¹¹⁴ Sentence per Modification 12 (Amendment 1)

	Integrated Clinical Study Pro	otocol
	BAY A2502 / 16027	
03 NOV 2020	Version 11.0	Page: 46 of 259

part 2 of the study (see Section 16.1).¹¹⁵ Antitrypanosomal treatment required during the course of LTFU at the discretion of the investigator is considered as concomitant medication. The following information will be entered in the eCRF: generic name of the medication, indication, dose, unit, frequency, route of administration, and start and stop date (if stopped before the end of study).

The ingestion of alcohol may increase the incidence and severity of undesirable effects of nifurtimox. Therefore, chronic abuse of alcohol and intake of alcohol or other alcohol-containing preparations during the study period are prohibited (applicable to part 1 only).

8.2 **Post-study therapy**

Study medication will not be continued after the study. Subsequent treatment should be discussed between the subject and/or the subject's legally authorized representative and the investigator during the final visit. At the end of this study, it is expected that the subject will receive standard treatment according to local clinical guidance.

9. **Procedures and variables**

9.1 Tabular schedule of evaluations

The schedule of procedures/assessments to be performed during part 1 (CHICO) of the study is presented in Table $9-1.^{116}$

The schedule of procedures/assessments to be performed during part 2 (CHICO SECURE) of the study is presented in Table 9–2.

¹¹⁵ Text modified for clarity, and sentence regarding concomitant medication assessment per Phone Contact Form added per Modifications 6 and 12 (Amendment 1)

¹¹⁶ Table revised to include a telephone assessment at Visit 4, and an assessment (Visit 5) prior to the Day 30 Visit as recommended (Modifications 6 and 8); wording of assessments expanded for clarity; diary dispense and collection added; coagulation added to serum laboratory assessments, and neurological assessment added per Modification 10; concomitant medications moved to appear earlier in table. Table footnotes revised and re-lettered according to changes made in text per Amendment 1 (Amendment 1). In addition, replaced IFA with IHA per Amendment 6.

03 NOV 2020

Version 11.0

Page: 47 of 259

Table 9–1: Schedule of procedures and assessments in part 1 – Study 16027

Phase	Screening			т	reatment	Phase			Follow-up Phase		
Visit	1	2	3	4 ^a	5 ^a	6	7 a	8 (EOT) ^b	9	10	11
Day	-14 to -1	1 ^c	7 ± 1	14 ± 1	21 ± 3	30 ± 3	42 ± 3	60 ± 3	90 ± 7	240 ± 7	420 ± 7
Initiation procedures							11				
Informed consent/assent	•										
Demographics (sex, age)	•										
Medical/surgical history	•										
Inclusion/exclusion criteria	•	•									
Efficacy											
Assessment of Chagas' disease signs and symptoms ^d	•		•			•		•	•	•	•
Concentration test for T. cruzi (subjects < 8 months of age)	•		•			•		•	٠		
Conventional and non-conventional serologic testing for	•		•			•		•		•	
Chagas' disease ^e	•		•			•		•		•	•
qPCR ^e	•		•			•		•		•	•
Indirect hemagglutination assay (IHA) *	•										•
Safety											
Adverse events	•	•	•	•	•	•	•	•	•	•	•
Concomitant medication	•	•	•	٠	•	•	•	•	•	•	•
Physical examination ^f	•		•			•		•	•	•	•
Neurological examination ^g	•		•			•		•			
Vital signs (heart rate, RR, BP, temperature), height/length,	•	•	•			•		•	•	•	
and weight h	•	•	•					•	•	•	•
12-lead ECG ⁱ	•	•	•			•		•	•	•	•
Serum hematology, chemistry, and coagulation ^j	● ^k		•			•		•	•		
Urinalysis (if specimen can be obtained)	●k		•			•		•	•		
Urine pregnancy test ¹	•	•	•			•		•	•		
Pharmacokinetics											
PK blood sampling (optional) ^m		•	•			•		•			
Study Treatment											
Study drug administration ⁿ		•				•					
Study drug and diary dispensed °		•				• p					
Study drug and diary collected			•			• p		•			
Study drug accountability/review compliance			•	•	•	•	•	•			
Dispense pre-paid phone card ^q			•			•					
Collect pre-paid phone card						•		•			

03 NOV 2020

Version 11.0

Page: 48 of 259

Table 9–1: Schedule of procedures and assessments in part 1 – Study 16027

Phase	Screening	Treatment Phase				Fol	Follow-up Phase				
Visit	1	2	3	4 ^a	5 ^a	6	7 ^a	8 (EOT) ^b	9	10	11
Day	-14 to -1	1 °	7 ± 1	14 ± 1	21 ± 3	30 ± 3	42 ± 3	60 ± 3	90 ± 7	240 ± 7	420 ± 7

BP = blood pressure, ECG = electrocardiogram, EOT = end-of-treatment, IHA = indirect hemagglutination assay, qPCR = quantitative polymerase chain reaction, PK = pharmacokinetic, RR = respiratory rate per minute.

^a At Days 14, 21, and 42, study site personnel will contact the subject/legally authorized representative via telephone to assess for the occurrence of adverse events, use of concomitant medications, and compliance with study drug administration. A Phone Contact Form for the telephone contacts to obtain safety and compliance information will be provided to all sites (see Section 16.1). If any safety concern arises, subjects may return to the study site for an Unscheduled Visit.

^b Subjects who discontinue prematurely from study drug administration will continue to return to the investigational site for study assessments at Visits 3, 6, and 8 (EOT), and undergo telephone assessments as described for Visits 4, 5, and 7. If subjects are unable/unwilling to do so, they must return to the investigational site 30 (±3) days after the last dose of study drug for EOT (Visit 8) assessments, and undergo telephone assessments as described for Visits 4, 5, and 7. If the subject is unable/unwilling to return to the clinic for the EOT Visit (Visit 8), then a telephone assessment as described for Visits 4, 5, and 7 may be performed in lieu of Visit 8 assessments.

^c All assessments are to be obtained pre-treatment on Day 1 except for post-dose PK blood sampling.

^d To be performed during physical examinations; see Section 9.4.4

^e Specimen taken for non-conventional ELISA, qPCR and stored (as per amendment 2)

^f A complete physical examination of body systems will be performed at the Screening Visit. A brief physical examination, including assessments of heart, lungs, and abdomen, skin for the presence of severe dermatitis, and assessments for the presence of peripheral neuropathy will be performed at all subsequent designated time points. Abnormal findings on physical examination at Screening will be documented as medical history; abnormal findings thereafter will be documented as AEs (see Section 9.6.1.1).

^g A neurological examination including assessments of mental status and cognition, cranial nerves, motor function, deep tendon reflexes, sensation, and coordination and gait will be performed. Abnormal findings on neurological examination at Screening will be documented as medical history; abnormal findings thereafter will be documented as AEs (see Section 9.6.1.1).

^h Blood pressure is optional in subjects < 5 years of age at the discretion of the investigator. Height/length and weight will be obtained with the subject wearing minimal clothing and no shoes.

ⁱ 12-lead ECG is optional in subjects < 5 years of age at the discretion of the investigator. At the 2 – 4 hour time point for PK blood sampling (i.e., at the time of maximum concentration), the ECG will be obtained to allow for PK/PD investigations.

¹ Fasting of subjects for serum laboratory assessments is dependent on the age of the subject at the discretion of the investigator.

^k Test conducted by local laboratories (as per amendment 2)

¹ Urine pregnancy tests will be performed on all females of childbearing potential (i.e., all female subjects who have experienced menarche). Any subject with a positive urine pregnancy test will have a serum pregnancy test to confirm results; if pregnancy is confirmed, the subject is to be discontinued from the study and undergo all study assessments as described in the EOT Visit.

^m Blood samples for pharmacokinetic parameters will be obtained prior to administration of study drug, and at designated time points thereafter (see Table 9–1). They are optional and require consent/assent of the subject/subject's legally authorized representative(s).

ⁿ Subjects consenting to optional PK assessments must withhold taking the morning dose of study drug on the day of Visits 3, 6, and 8. Subjects not consenting to optional PK assessments may take their study drug on the mornings of Visits 3, 6, and 8 as instructed.

^o Depending on the country, study site personnel may dispense condoms at the time that study drug is dispensed to either the subject or the subject's parent/legal guardian, with an explanation of rationale and risks.

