will be dispensed, instructions for study drug administration will be provided, and diaries with instructions for completion will be given⁵⁷, to all subjects.⁵⁸

Subjects will return to the investigational site for efficacy and safety assessments at Visits 3 (Day 7±1) and 6 (Day 30). Subjects who have not consented to PK assessments will take that day's doses of study drug as instructed. Subjects consenting to PK assessments must hold the morning dose of study drug; for these subjects, a pre-dose PK blood sample will be obtained, then the morning dose of study drug will be administered with food and the PK diary completed.⁵⁹ Post-dose blood samples will be obtained at specified time points, and ECGs will be obtained at the 2 - 4 hour post-dose time point (see Table 9–1). A pre-paid phone card will be provided to all subjects to facilitate contact between study site personnel and the subjects/subjects' authorized representatives.⁶⁰

At Visit 6 (Day 30), subjects will return all remaining study drug and empty packaging, and study drug for the remaining 30 days of treatment, along with subject diaries, will be dispensed.⁶¹

Visits 4 (Day 14), 5 (Day 21), and 7 (Day 42) will be telephone assessments where study site personnel will contact the subject/legally authorized representative via telephone to assess the occurrence of AEs, use of concomitant medications, and compliance with study drug administration, and completion of subject diary. A Phone Contact Form for the telephone assessments will be provided to all sites (see Section 16.1).⁶²

Subjects will return to the investigational site for efficacy and safety assessments on Day 60 (Visit 8), which will be the EOT for both treatment groups. Subjects who have not consented to PK assessments will take that day's doses of study drug as instructed. Subjects consenting to PK assessments must hold the morning dose of study drug. A pre-dose PK blood sample will be collected, then the morning dose of study drug will be administered with food, and the subject will complete the PK diary. Post-dose PK blood samples will be obtained at specified time points, and ECGs will be obtained at the 2 - 4 hour post-dose time point (see Table 9–1). Study drug will be collected, and no additional study drug will be dispensed.⁶³

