After the EOT visit (Visit 8), subjects will return to the site on Days 90 (Visit 9), 240 (Visit 10), and 420 Visit 11) for additional efficacy and safety assessments. The total duration of each subject's participation is expected to be approximately 14 months.⁶⁴

Assessments of efficacy and PK will be performed at specified time windows. In order to minimize the burden of blood loss due to PK sampling, age-appropriate sparse sampling strategies combined with (micro-)bioanalysis techniques will be applied (see Table 9–5). At

⁵⁷ Text modified as per amendment 4

⁵⁸ Text added for clarity and per Modification 1 (Amendment 1)

⁵⁹ Text modified as per amendment 4

⁶⁰ Text modified/added for clarity and per Modification 1 (Amendment 1)

⁶¹ Text added for clarity (Amendment 1)

⁶² Text added for clarity and per Modifications 6 and 8 (Amendment 1)

⁶³ Text modified/added for clarity and per Modification 1 (Amendment 1)

⁶⁴ Text modified for clarity (Amendment 1)

	Integrated Clinical Study Protocol	
	BAY A2502 / 16027	
03 NOV 2020	Version 11.0	Page: 30 of 259

least 10 subjects per age stratum should ideally be recruited for PK assessments.⁶⁵ Recruitment of less than 10 subjects per age group is not considered as a protocol violation.⁶⁶

Safety will be assessed via laboratory parameters (hematology, blood chemistry, urinalysis), vital sign measurements (blood pressure [optional in subjects < 5 years of age at the discretion of the investigator], heart rate, respiratory rate, temperature), monitoring of ECGs (optional in subjects < 5 years of age at the discretion of the investigator), monitoring of AEs, and physical examinations, including a neurological examination (see Section 9.6.3.3).⁶⁷

Subjects who discontinue prematurely from study drug administration will continue to return to the investigational site for study assessments at Visits 3, 6, and 8 (EOT), and undergo telephone assessments as described for Visits 4, 5, and 7. If subjects are unable/unwilling to do so, they must return to the investigational site 30 (\pm 3) days after the last dose of study drug for EOT (Visit 8) assessments, and undergo telephone assessments as described for Visits 4, 5, and 7. If the subject is unable/unwilling to return to the clinic for the EOT Visit (Visit 8), then a telephone assessment as described for Visits 4, 5, and 7 may be performed in lieu of Visit 8 assessments.⁶⁸

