6.3.1 Withdrawal

Withdrawal criteria

Subjects *must* be withdrawn from the study if any of the following occurs:

• At their own request or at the request of their parents' or legally acceptable representative. At any time during the study and without giving reasons, a subject may

	Integrated Clinical Study Protocol	
	BAY A2502 / 16027	
03 NOV 2020	Version 11.0	Page: 40 of 259

decline to participate further. The subject will not suffer any disadvantage as a result of this decision.

- Pregnancy. If any urine pregnancy test is positive, a serum pregnancy test must be performed to confirm the result. See Section 9.6.2.⁹⁴ (not applicable to part 2)
- Subjects, with positive parasitology test at the 30-day visit for whom (1) it has been determined that the drug was administered correctly and (2) the daily dosage given was correct, must be discontinued from the study and treated with an alternative trypanocidal medication, selected by the investigator.⁹⁵ (not applicable to part 2)

Subjects *may* be withdrawn from the study if any of the following occurs:

- If, in the investigator's opinion, continuation of the study would be harmful to the subject's well-being
- At the specific request of the sponsor and in liaison with the investigator (e.g., obvious non-compliance, safety concerns)
- For the following situations that are regarded by the investigator to be related to the use of study drug (nifurtimox) (not applicable to part 2):
 - Severe nervous system disorders such as seizure, vertigo/dizziness, polyneuropathy, or peripheral neuropathy
 - Severe gastrointestinal disorders, severe decreased appetite
 - Significant loss of body weight in the judgment of the investigator
 - Severe hepatic impairment
 - Severe renal impairment
 - Psychic disorders such as disorientation, psychotic behavior
 - Development of malignant disease
 - Hematological abnormalities such as severe leukopenia

Depending on the time point of withdrawal, a withdrawn subject is referred to as either "screening failure" or "dropout" as specified below:

Screening failure

A subject who, for any reason (e.g., failure to satisfy the selection criteria), terminates the study before the time point used for the definition of "dropout" (see below) is regarded as a "screening failure."

Re-starting the defined set of screening procedures to enable the "screening failure" subject's participation at a later time point is allowed only in the following situations (not applicable to part 2):

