03 NOV 2020

Page: 57 of 259

discontinued from the study and undergo all study assessments as described in the EOT Visit.

- For subjects consenting to PK assessments, a pre-dose PK blood sample will be obtained (see Table 9–1).
- Administer study drug with food to subjects consenting to PK assessments (who withheld their morning dose of study drug), and instruct subject on completion of PK diary, according to the instructions provided on the PK subject diary.¹³³
- For subjects consenting to PK assessments, post-dose PK blood samples will be obtained (see Table 9–1). At the 2 4 hour time point (i.e., at the time of C_{max}), an ECG will be obtained.
- Collect study drug, diary, and pre-paid phone card

Version 11.0

• Drug accountability and review of diaries for study drug compliance and for PK subjects, documentation of meals during study drug administration.^{134,135}

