03 NOV 2020

Page: 58 of 259

• Urine pregnancy test on all females of childbearing potential (i.e., those who have experienced menarche). Any subject with a positive urine pregnancy test will have a serum pregnancy test to confirm results. See Section 9.6.2.¹³⁶

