9.6.2 Pregnancies

Part 1 (CHICO)

Any subject who becomes pregnant during the course of the study will discontinue study treatment. Pregnancy must be confirmed by serum pregnancy test. The investigator must report to the sponsor any pregnancy occurring in a female study subject during her participation in this study. The outcome of the pregnancy should be followed up carefully, and any outcome of the mother and the child at delivery should be reported.

For a pregnancy in the partner of a male study subject, all efforts will be made to obtain similar information on course and outcome, subject to the partner's consent and any abnormal outcome of the child should be reported.

For all reports, the forms provided are to be used. The investigator should submit them within the same timelines as an SAE.

Part 2 (CHICO SECURE)

At each visit in part 2, female subjects will be asked if she is pregnant or gave birth to a baby after the first dose of nifurtimox treatment regimen or since the last visit.

The investigator must report to the sponsor any pregnancy occurring in a female study subject during her participation in this study. The outcome of the pregnancy should be followed up carefully, and any outcome of the mother and the child at delivery should be reported.

Female subjects who give birth by the end of part 2 of the study will be invited to test their child for the absence or presence of infection with *T. cruzi*, except if the child was already tested according to the standards of the country or has already received treatment for Chagas' disease. The congenital infection will be confirmed by parasitological method in children ≤ 8 months of age and by serological method in children >8 months of age. Efforts should be made to obtain the results of congenital infection testing when already done according to the standards of the country. The result of congenital infection will be documented in the applicable eCRF form.

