9.6.3.6 Urine pregnancy test

A urine pregnancy test on all female subjects of childbearing potential (i.e., all females who have experienced menarche) will be performed at screening and Visits 2, 3, 6, 8 (EOT), and 9 (Follow-up). If any urine pregnancy test is positive, a serum pregnancy test will be performed to confirm the result. If pregnancy is confirmed at Visits 1 or 2, the subject is to be excluded from study participation. If pregnancy is confirmed at Visits 3 or 6, the subject will be discontinued from the study (See Section 9.6.2) and undergo all study assessments as described for the EOT Visit (Section 9.2.2.7).¹⁷⁸

There will be no urine pregnancy test in part 2 of the study.

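### The Part 1 pregnancy rules conflict at Visits 8 and 9, and the stricter reading discards a 12-month serology result that could be kept

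*Protocol*

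**What the plan says.** Three places in the protocol take the girl out of the study.

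- **Section 6.3.1** lists pregnancy among the mandatory reasons for withdrawal, with no visit limit and an exemption for Part 2 only: "Pregnancy. If any urine pregnancy test is positive, a serum pregnancy test must be performed to confirm the result. See Section 9.6.2".
- **The Table 9-1 footnote** to the pregnancy-test row, which is marked at Visits 1, 2, 3, 6, 8 and 9, says "if pregnancy is confirmed, the subject is to be discontinued from the study and undergo all study assessments as described in the EOT Visit".
- **Section 9.2.2.7 (Visit 8)** repeats it: "discontinued from the study and undergo all study assessments as described in the EOT Visit".

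Three places say less.

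- **Section 9.6.2**, to which the 6.3.1 bullet itself refers, says for Part 1: "Any subject who becomes pregnant during the course of the study will discontinue study treatment".
- **Section 9.6.3.6** lists tests at Visits 8 and 9 but gives a study discontinuation only for two earlier visits: "If pregnancy is confirmed at Visits 3 or 6, the subject will be discontinued from the study".
- **Section 9.2.3.1 (Visit 9)** says only: "Any subject with a positive urine pregnancy test will have a serum pregnancy test to confirm results. See Section 9.6.2".

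On timing, Section 5.1 says of Visit 8: "Study drug will be collected, and no additional study drug will be dispensed". It then schedules the follow-up: "After the EOT visit (Visit 8), subjects will return to the site on Days 90 (Visit 9), 240 (Visit 10), and 420".

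On analysis, protocol 10.3.2.1 and SAP 4.3 count a missing 12-month serology in the FAS as a failure.

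**The concern.** Stopping drug in a pregnant girl needs no defence. At Visit 8, however, the last supply has been collected, and at Visit 9 treatment has been over for about a month. Withdrawal at either visit removes no exposure; it removes follow-up. What is lost is the Day 420 sample that carries the primary endpoint. The analysis then fills the gap with a failure that says nothing about whether the drug worked.

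The conflicting wording also means that two sites could handle the same event differently. One would record a treatment failure and the other an observed result.

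**Working it through.** **1. The texts side by side**

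| Place in the protocol | Visit 8 | Visit 9 |
|---|---|---|
| 6.3.1 | withdraw from study | withdraw from study |
| Table 9-1 footnote | discontinue from study | discontinue from study |
| The visit's own text | discontinue from study | confirm, see 9.6.2 |
| 9.6.2, Part 1 | stop treatment | stop treatment |
| 9.6.3.6 | no action given | no action given |

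The weight of text favours withdrawal at Visit 8 and is more evenly divided at Visit 9. Neither visit is free of conflict.

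**2. What follows if she is withdrawn**

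- No section provides for Visit 10 or 11 after withdrawal from the study. That the Day 420 sample is not taken is an inference from this, though the natural one.
- FAS primary analysis: failure (protocol 10.3.2.1, SAP 4.3).
- First sensitivity analysis in SAP 6.2.1.1: still a failure, unless she had a negative serology at an earlier visit or her missing value falls under none of the listed reasons.
- Observed-data and per-protocol analyses: excluded.
- Recovery: SAP 4.5 bars unscheduled post-baseline values. She may enter Part 2, for which one dose suffices (6.1), but its first serology is scheduled at year 2 (Table 9-2).

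**3. The plan's own figure**

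Inputs: n = 200 in the 60-day arm, cure rate 55% and threshold 16% (protocol 10.4), with the interval of SAP 6.2.1.1:

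lower limit = p − 1.96·√(p(1−p)/n) − 1/(2n)

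- The smallest number of cures that passes is 44. At p = 44/200 = 0.22 the limit is 0.22 − 0.0574 − 0.0025 = 0.1601. At 43 cures it is 0.1556.
- The exact binomial probability of at least 44 cures at 55% exceeds 99.99%, so the stated 99% power is met.

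**4. Size per case**

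A girl who would have been cured but is scored as no cure costs 1/200 = 0.5 points. Weighted by the planned cure rate:

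- 60-day arm: 0.55 × 1/200 = 0.275 points
- 30-day arm (n = 100): 0.55 × 1/100 = 0.55 points

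The documents give no number of pregnancies, so the counts below are assumptions. They use p = 0.55 × (1 − k/200) for k cases in the 60-day arm.

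| Assumed k | Expected rate | Lower limit at that rate |
|---|---|---|
| 0 | 55.00% | 47.86% |
| 1 | 54.73% | 47.58% |
| 4 | 53.90% | 46.74% |

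**5. Against the decision lines**

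- 16% test: 110 cures are planned and 44 needed, so 66 could be lost before it failed.
- Exploratory benznidazole line of 45% (SAP 6.2.1.3): 105 cures are needed. With one assumed case the chance of passing falls from 78.3% to 76.0%.
- Difference between regimens: with equal pregnancy rates, for example 2 and 1 cases, 0.55 × (1 − 2/200) − 0.55 × (1 − 1/100) = 0. The expected difference is unchanged.

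**The case against.** A reader might infer that the protocol settles the matter at Visit 8, so that every such girl is lost, and that only Visit 9 is unclear. The documents do not support that. Sections 9.6.2 and 9.6.3.6, which unsettle Visit 9, apply equally to Visit 8. The withdrawal sentence also looks generic. It is the same at Visits 3, 6 and 8, and at Visit 8 its call for end-of-treatment assessments is redundant because she is already at that visit. Read literally, the footnote also covers Visits 1 and 2, where the visit texts speak of exclusion. A site could therefore reasonably keep her. This objection stands, and the loss is conditional on how sites read the rules.

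The case against materiality is also strong. Eligible cases are post-menarche girls who tested negative through Visit 6, under a contraception requirement that runs to three months after the last dose (6.1). Failure imputation is prespecified and applies to every missing 12-month value. The 55% rate is probably too high for these girls, since Section 5.1 reports that 20% sero-reduction at 12 months was more common in younger children. All of this limits the size. None of it gives a reason to discard the sample.

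Finally, the remedy may come too late. Protocol Version 11.0 is dated November 2020 and its latest amendment concerns Part 2. The documents do not say whether Part 1 follow-up has closed.

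**Conclusion.** The conflict is real at both visits. Under the withdrawal reading it costs an avoidable primary-endpoint value. The bias runs against the drug and is very small: at most about 0.275 points expected per case in the 60-day arm, assuming the planning rate of 55% applies to these girls and that withdrawal means no Day 420 sample. The number of cases is unknown and likely very small.

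A reader might also infer a threat to the primary conclusion. There is none, because the margin is 66 cures. The 45% comparison is more sensitive, but it is exploratory, and any multi-case scenario for it rests on counts that the documents do not supply.

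This is a low-priority improvement. It is worth making because the lost value serves no safety purpose: Visits 10 and 11 involve no study drug, 9.6.2 already follows the pregnancy, and Part 2 draws blood at its annual visits without treating pregnancy as a reason for withdrawal.

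**What to change.** Amend Section 6.3.1, the Table 9-1 footnote and the Visit 8 and Visit 9 texts to say one thing: a pregnancy confirmed after the first dose stops any remaining study drug but does not withdraw the girl from the study, and scheduled serology at Visits 10 and 11 is still collected unless consent is withdrawn. Keep exclusion for a pregnancy found at Visits 1 or 2, and leave the 9.6.2 reporting and outcome follow-up unchanged. Extending the wording to Visits 3 and 6, with 9.6.3.6 aligned, follows the same logic but is optional, since the visit texts there agree with the withdrawal rule and dosing is still under way.

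The cost is a protocol amendment with the approvals that Section 13.1 requires at each center, and possibly a revised consent form under 13.4. It adds no visit, test or procedure. The gain in data applies only to girls still in Part 1 follow-up; if there are none, the change serves only as clarification.
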